This study uses a blocked randomized controlled design. The study subjects will be selected using a convenience sampling method. When selected, the subjects will be randomly assigned to either one of the 4 study groups using a stratified random strategy (stratifying variable= academic year of study). The study groups (PMR, MM, GI, Control group) will received 5 30-minute weekly sessions of their assigned intervention over 5 weeks. However, there will be a 4-hours workshop explaining the purposes and techniques of the study interventions before introducing the actual session. The subjects will be asked and encouraged to practice their assigned intervention for 30 minutes daily at home. The dependent variables will be measured three times for the 4 groups: at baseline, at the middle (after the second session), and at the end of intervention.

Participants

Participants are undergraduate nursing students who will be selected using a stratified random sampling method from Jordan University of Science and Technology. Jordanian undergraduate nursing students will be asked to participate in the current study if they are at least 18 years old and taking a clinical course. Exclusion criteria include students who are 1) practicing of any type of relaxation techniques, such as yoga, guided imagery, meditation, cognitive behavioral therapy, or 2) taking hypnotics, sedatives, anxiolytic, anti-depressant, anti-inflammatory drugs.

Determination of Sample Size

Using G* Power software 3.1, mixed-design (within groups-between groups) repeated measures ANOVA, an alpha of .05, a power of 0.8, the number of measurements of 3, the number of groups of 4, and a moderate effect size of 0.25, the sample size of 180 was generated. A 15 % attrition rate was reported in a previous study with variables similar to the present study [14]. Considering an expected attrition rate of 15 %, the required final total sample size 210.

Intervention

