Control Group. Participants in the control condition will be instructed to sit with their eyes closed during the intervention periods. Participants in the control group will follow an identical time period as the experimental groups. For instance, when the experimental groups will practice for 30 minutes, the participants in the control group will be asked to sit with eyes closed and relax for 30 minutes.

Procedure

First, approvals from the JUST institutional review boards will be obtained. After that, a translation from English to Arabic and pilot testing of the English versions of the scales used in the current study will be performed. The scales used in the study will be introduced for 30 Jordanian undergraduate nursing students, and then the construct validity, reliability (internal consistency), readability of these scales will be examined.

After taking the permission of the dean of nursing college and class's instructors, the PI will visit students in their classrooms. As the lecture finishes, The PI will announce the

title and objectives of the study and ask the students who would like to participate to contact him using a business card including the PI's contact information (his name, phone number, and email) given for each one. The contact information will be used only for the purpose of the study. The PI will arrange an initial meeting to meet with students who would like to participate on another day in a private room at the university. At this meeting, the PI will inform the students the study's objectives, risks, benefits, and confidentiality and answer questions that they have about the study. Also, they will be assured that they have the full right to refuse or discontinue the participation at any time and that such refusal or discontinuation will not affect their academic achievements in any way. If agree to participate and eligibility criteria are met, informed consent will be obtained at the meeting. After that, the participants will be randomly assigned equally to the study groups using a stratified random assignment method (stratifying variable= academic year of study). Finally, dates and times for sessions will be set up and sent to the participants using their e-mails.

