For the physical variables. The Enzyme-linked Immunosorbent Assay (ELISA) procedure will be used to measure serum biomarkers such as cortisol, melatonin, C-reactive protein, interleukin 1, and Leptin.

Cognitive Responses

Executive Functioning. Executive functioning is a set of inter-related higher-order cognitive abilities involved in self-regulatory functions that organize, direct, and manage cognitive activities, emotional responses, and overt behaviors (Barkley, 2011). The Barkley Deficits in Executive Functioning Scale- Short form (BDEFS-SF) (Adult version) will be used to measure executive functions including self-organization, self-restraint, self-motivation, self-regulation of emotion, and self-management to time. It is a self-reported scale consisting of 20 items measured using a 4-point Likert-type scale, ranging from Never or rarely (1) to Sometimes (2), Often (3), and Very often (4). The BDEFS-SF internal consistency was reported at an alpha of .92 in adult population. A confirmatory factor analysis supported the 5-factor structure of BDEFS in college students (19).

Mindfulness. Mindfulness is defined as open or receptive awareness of and attention to what is taking place in the present (20). Mindful Attention Awareness Scale (MAAS) will be used to measure dispositional mindfulness. It is one-dimensional scale including 15 items

measured on a six-point Likert type scale, ranging from 1 (almost always) to 6 (almost never). The score range is between 15 and 90, with higher score indicating higher levels of mindfulness. The scale has shown strong psychometric properties when validated in college students. It showed acceptable levels of reliability and validity in university students (20).

Perceived Stress. The Perceived Stress Scale (PSS) is used to measure the degree to which situations in one's life are appraised as stressful (unpredictable, uncontrollable, and overloaded). It includes 10 items measured on a 5-point Likert scale (0=never, 4= very often), which are relatively free of content specific to any subpopulation group. The scores range from 0 to 40 with higher score indicating higher levels of perceived stress (21). PSS has been validated for use with college students (21).

Emotional Responses

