Statistical analysis will be conducted using SPSS software (version 23). Descriptive statistics will be used to describe the sample. The sample and variables will be described by measures of central tendency and dispersion appropriate to the level of measurement. Initial analyses will be conducted to ensure that the randomization across covariates was successful. The gender, marital status, employment, nationality, and smoking behavior variables will be all tested at baseline using Chi-square to demonstrate that they are not significantly different

between groups. Independent t-tests will be run at baseline measurements of dependent variables to make sure the study groups will be not significantly different on these variables before introducing the study intervention. One-way- ANOVA will be used to test the study hypotheses. Post hoc t-tests will be run to examine if the study groups will be significantly different on the dependent variables at end of the intervention. In case of having confounding effects of some variables, ANCOVA will be used.

Ethical consideration

Physical or psychological harm or risks that might be associated with the measurement activities or intervention employed in the current study will be minimal. One risk that might have resulted from the study was making demands on the subject's time and venipuncture-related pain. Thus, the subjects were provided with compensations (10 Jordanian Dinars) for their times spent in the study and ELMA cream will be used before blood sampling to decrease venipuncture-related pain. Moreover, trained nurses will draw blood from participants, following the Blood Sampling Guideline of the European Federation of Clinical Chemistry and Laboratory Medicine, 2017.

Potential benefits of the measurement activities and intervention to study subjects included increased knowledge and awareness about their health and mind-body modalities. For society, potential benefits included a greater understanding of the effects of mind-body modalities on stress reduction and the potential improvement of the study population's health. In this study, potential benefits are believed to exceed risks.

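### The plan sets no analysis scale for the ELISA biomarkers and adjusts for covariates only if confounding appears; log-scale ANCOVA on baseline would protect and raise power at little cost

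*Combined protocol and SAP*

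**What the plan says.** All references are to the combined protocol and SAP.

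- **Instruments** says that ELISA "will be used to measure serum biomarkers such as cortisol, melatonin, C-reactive protein, interleukin 1, and Leptin". **Physical Responses** lists the same markers as outcomes. No section gives an SD, coefficient of variation, skewness or expected change for any of them.
- **Statistical Analysis** states: "One-way- ANOVA will be used to test the study hypotheses". Post hoc t-tests at the end of intervention follow, and ANCOVA is held back for confounding. No transformation, distribution check, non-parametric alternative or rule for undetectable values appears. The section is silent on transformation; it does not exclude it.
- **Determination of Sample Size** names a "mixed-design (within groups-between groups) repeated measures ANOVA" for four groups and three time points, at 5% alpha and 80% power. It assumes "a moderate effect size of 0.25" and arrives at 180 before attrition. It ties the effect size to no outcome and no scale.
- **Procedure** states that "the participants will be randomly assigned equally to the study groups", which gives 45 per arm at 180. It also has the dependent variables measured at baseline, after the second session and after the fifth.

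**The concern.** The biomarkers are the only objective outcomes listed; every other outcome is a questionnaire score. Concentrations may be right-skewed. If they are, a few high values inflate the raw-scale within-arm variance, and a proportional effect becomes harder to detect.

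The pattern most exposed is one arm lower than the rest. The Introduction makes that pattern plausible for a marker such as cortisol: it expects progressive muscle relaxation to do better on physical health, and it treats raised cortisol as harmful.

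Two things are at stake. The scale is not fixed in advance, so it is either raw by default or open to choice after the data are seen. And the baseline measurement, already collected, is not used routinely to gain precision.

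**Working it through.** **Step 1: reproduce the plan's figure.** Inputs from Determination of Sample Size: alpha 0.05, power 0.80, f = 0.25, 4 groups. For a one-way ANOVA the noncentrality is λ = f²N with 3 and N − 4 degrees of freedom. At N = 180, λ = 0.0625 × 180 = 11.25 and power is 0.804. The smallest N reaching 0.80 is 179, so 180 with equal arms. The figure therefore reproduces as a one-way ANOVA. It does not match the mixed-design test that the section names (at an assumed correlation of 0.5: 40 for the interaction, 124 for the between-group factor). That mismatch is a separate matter, but it makes 45 per arm the right base for checking a one-way test.

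**Step 2: what f = 0.25 means on the log scale.** If one arm differs by d log-SDs from the other three, the SD of the four means is d × √3/4. Setting this to 0.25 gives d = 0.25 × 4/√3 = 0.577. The ratio of geometric means is exp(±0.577 × log-SD), so holding f fixed implies a larger ratio as the log-SD rises.

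**Step 3: raw-scale against log-scale ANOVA.** Assumptions, none given in the documents: log-normal values, a proportional effect with f = 0.25 on the log scale, and the log-SDs shown. Trials of 4 × 45 were simulated and the 5% F test was applied to raw values and to logs. The last column is a repeat run of 20,000 trials per setting.

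| Log-SD | Implied ratio, one arm higher / lower | Power on logs | Raw power, range | Repeat: one higher / one lower |
|---|---|---|---|---|
| 0.3 | 1.19 / 0.84 | 0.80 | 0.76–0.80 | 0.80 / 0.76 |
| 0.5 | 1.33 / 0.75 | 0.80 | 0.72–0.78 | 0.77 / 0.71 |
| 0.8 | 1.59 / 0.63 | 0.80 | 0.58–0.71 | 0.70 / 0.58 |
| 1.0 | 1.78 / 0.56 | 0.80 | 0.48–0.65 | 0.64 / 0.47 |

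The runs agree to about 0.01. Evenly spaced arm means fall between the two patterns. Control higher than all three active arms is the one-arm-higher pattern.

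**Step 4: checks that limit the claim.**

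- Type I error of raw-scale ANOVA on log-normal data: 0.046 to 0.051 up to log-SD 0.5, about 0.04 at 1.0 and about 0.03 at 1.5.
- If f = 0.25 is an additive shift on the raw scale, raw-scale power is about 0.80 to 0.81 up to log-SD 0.5 and 0.82 to 0.84 at 1.0.

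**Step 5: gain from baseline adjustment.** With correlation r between log baseline and log outcome, residual variance falls by the factor 1 − r², so λ = 11.25/(1 − r²) with 3 and 175 degrees of freedom. The correlations are assumptions.

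| r | λ | Power |
|---|---|---|
| 0 (no adjustment, Step 1) | 11.25 | 0.80 |
| 0.3 | 11.25/0.91 = 12.36 | 0.84 |
| 0.5 | 11.25/0.75 = 15.00 | 0.91 |
| 0.7 | 11.25/0.51 = 22.06 | 0.98 |

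**The case against.** The strongest case on the other side is that the loss rests on inputs the documents do not supply: log-normal values, a sizeable log-SD, and an effect size defined on the log scale. Being bounded at zero does not establish skew, since several questionnaire scores share that bound. The larger losses also come with large assumed effects: at log-SD 1.0 one arm must have 0.56 or 1.78 times the geometric mean of the others. And the 80% belongs to no biomarker. All of this stands, and it makes the loss conditional.

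The additive-shift result stands too, but it does not favour the raw scale. For log-normal data with upward additive shifts of that size, log-scale power was simulated at 0.96 at log-SD 0.5 and above 0.99 at 0.8 and 1.0. A downward shift of that size in one arm would make about 36% of its values negative at log-SD 0.8 and 59% at 1.0, which concentrations cannot be.

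A reader might also infer that raw-scale analysis brings no benefit. That is not so: it compares arithmetic means in original units, a different estimand, and it needs no special handling of zeros. Nor can one infer that extreme values would produce excess false positives; Step 4 shows a test at or below its nominal level.

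**Conclusion.** The point holds in a conditional form. The plan leaves the biomarker scale unstated and uses ANCOVA only if confounding is found. If a marker is right-skewed and effects are proportional, raw-scale ANOVA gives up about 0 to 4 points of power at log-SD 0.3, 2 to 8 at 0.5, 9 to 22 at 0.8 and 15 to 32 at 1.0, relative to 80% on logs.

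It would be tempting to say that the trial's biomarker tests lose much of their planned 80% power. The documents do not support that: they give no distributions, name no outcome or scale for the effect size, and do not rule out a transformation. The loss is small for mildly skewed markers, and there is none relative to 80% under an additive raw-scale effect of the stated size.

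The case for change does not depend on strong skew alone. Routine baseline adjustment raises power whenever baseline and outcome are correlated, and fixing the scale beforehand removes a choice that could otherwise follow the data.

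**What to change.** In Statistical Analysis, state that the ELISA biomarkers (cortisol, melatonin, C-reactive protein, interleukin 1 and leptin) are analysed by ANCOVA on the natural-log scale, always adjusted for the log baseline value and not only when confounding is suspected. Report geometric mean ratios between arms with confidence intervals. State how values below the detection limit are handled, since logs cannot take zeros. Keep raw-scale ANOVA as a sensitivity analysis. The marker list should be closed at the same time, because Instruments names interleukin 1 while Physical Responses refers to interleukins in general.

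The cost is a few sentences: no extra participants, samples or visits. The real downside is interpretive: the primary biomarker results become ratios of geometric means instead of differences in arithmetic means, and only the sensitivity analysis stays in original units.

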In the 4-hour education session, the baseline measurements of the study variables will first be obtained. Then the PI will separately provide a power point presentation to participants in each experimental group as explained previously. At the end of the workshop, to avoid experiment contamination, the participants in each experimental group will be asked not to share any information related to the intervention with subjects in other groups.

The actual training will be introduced to subjects in the experimental groups, using an audio CD designed and produced by the PI based on the Smith's (2005) guidelines and protocols. Based on the ABC Relaxation Theory (Smith, 2005), at least two, and preferably five sessions of actual mind-body training should be provided to evoke relaxation and optimize health [15]. In the proposed study, the dependent variables will be measured at the middle and at the end of intervention to see whether further health benefits occur between these two measurements. The sessions will be provided to the study groups in a private, quiet,

comfortable, and spacious room at the university. The dependent variables will be measured three times for the groups: at baseline, after 2nd actual training session, and at the end of intervention (after 5th session), as mentioned previously.

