Various strategies will be followed to decrease measurement errors potentially affected by variations of data collection procedure. For example, filling out the questionnaire may be stressful for some subjects and, in turn, influences objective measures. Therefore, the self-reports measures will be completed after taking the objective measures such as biological markers. Also, all study measurements in the intervention and control groups will be undertaken in the same conditions (i.e., same room temperature and environment) by well-trained nurses as much as possible. The ELISA protocol, including blood sampling will strictly be followed. The neurotransmitters/hormones will be measured between 8:30 am and 9:30 am for all subjects at sitting position. Drinking coffee, tea, and having should be avoided 6 hours before the measurement of neurotransmitters/hormones. To decrease venipuncture-related pain during blood sampling, EMLA cream will be used, which has been found effective in decreasing venipuncture-related pain in different populations [17]. In addition, quiet environments, free from distraction, will be maintained with a “Do Not Disturb” sign on the door of the rooms during the intervention and data collection.

Instruments

The study data will be collected using self-reported and physical measures. For the self-reported variables, the study will use a self-reporting questionnaire in 6 main parts. The first part includes questions about smoking behaviors and demographic characteristics including: age, religion, gender, marital status, academic year of study, nationality, history of medical or psychiatric illnesses, and smoking behaviors. The second part includes scales used to measure cognitive responses such as executive function, mindfulness, and perceived stress.

The third part involves scales used to measure emotional health such as anxiety and depression. The fourth part includes a scale used to measure physical symptoms. The fifth part includes scale used to measure coping behaviors. The sixth part includes a scale used to measure fear-related injection. The seventh part includes open-ended questions focusing on the students' experiences of practicing their assigned intervention. The last three parts will be measured to examine the confounding effects of coping behaviors and fear associated with blood sampling on the study outcomes.

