Coping Behaviors. Nursing students’ self-directed coping behaviors included in the current study as a covariate were assessed by the Coping Behaviors Inventory (CBI) (28). The CBI is used to identify nursing students’ coping behaviors. It includes nineteen 5-point Likert-type items divided into four factors: avoidance behavior (efforts to avoid a stressful situation), 6 items; problem-solving behavior (efforts to manage or change the stress arising out of a stressful situation), 6 items; optimistic coping behavior (efforts to keep a positive attitude toward the stressful situation), 4 items; and transference behavior (efforts to transfer one’s attention from the stressful situation to other things), 3 items. Higher scores for each factor indicate more frequent use and greater effectiveness of a certain type of coping behavior. It showed acceptable levels of reliability and validity in nursing students (28)

Experiences of practicing the study interventions

Open-ended questions asking about the students experiences of practicing the PMR, GI, or MM?" will be added to the questionnaire packet at the end of study. The objective of these questions is to explore the narratives as provided by the subjects in the experimental groups. Findings from this question will help the principal investigators to understand any positive and/or negative reactions on the study interventions based on the subjects' feedback, thus, benefiting a plan for future larger research. Examples of these questions includes (29):

1. What did you think about the (assigned intervention)?
2. What did not like most about (assigned intervention)?
3. What did like most about (assigned intervention)?
4. Do you think (assigned intervention) were effective and worked for you?
 - a. If no, please could you explain why it did not work for you?
 - b. If yes, please could you explain how it worked for you?
5. Was the length okay? Would you have preferred longer, shorter, or the same?
6. Were there any obstacles of practicing (the assigned intervention) at home?

Statistical Analysis

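### The trial is sized on a three-measurement mixed ANOVA but analysed by a one-way ANOVA, so the stated mid-to-end question has no analysis and baseline values are not used to gain precision

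*Combined protocol and SAP*

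**What the plan says.** - **Determination of Sample Size** names a "mixed-design (within groups-between groups) repeated measures ANOVA, an alpha of .05, a power of 0.8, the number of measurements of 3", with four groups, and gives "a moderate effect size of 0.25, the sample size of 180 was generated". It does not say which effect was tested (between groups, within, or interaction), nor what correlation or sphericity value was entered.
- **Design and Procedure** place the outcome measurements at baseline, after the second session and after the fifth. The Procedure gives the reason for the last two: "to see whether further health benefits occur between these two measurements".
- **Statistical Analysis** says "One-way- ANOVA will be used to test the study hypotheses". That sentence gives no time point. The next one describes post hoc t-tests of whether the groups are "significantly different on the dependent variables at end of the intervention". Baseline outcomes appear only in t-tests of balance. The section ends: "In case of having confounding effects of some variables, ANCOVA will be used".
- **Instruments** says that some questionnaire parts are collected "to examine the confounding effects of coping behaviors and fear associated with blood sampling on the study outcomes". **Covariates** describes "self-directed coping behaviors included in the current study as a covariate were assessed by the Coping Behaviors Inventory". The Statistical Analysis section does not say how either variable enters a model.

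**The concern.** The two sections name different tests. A one-way ANOVA uses one value per student, whereas the test named for sizing uses three. The practical consequence lies in the middle measurement. Students give blood and complete questionnaires after session 2 so that a specific question can be answered, yet the analysis section has no repeated-measures term, no time effect and no change score. The Procedure also leaves open whether further benefit means change within a group or a difference in change between groups.

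The second matter is adjustment. The baseline value of each outcome is collected but not planned as a covariate. The switch to ANCOVA has a condition in words but no criterion and no final covariate list, so the model for each outcome would be settled after the data are seen. At stake are one unanswered study question and some avoidable loss of precision.

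**Working it through.** **Inputs from the protocol:** 4 groups, equal allocation, 3 measurements, alpha 0.05, target power 0.80, effect size 0.25 (taken as Cohen's f), 180 evaluable students, so 45 per group. **Assumed:** all correlations and the sphericity value epsilon, because the documents give none; ranges are shown. Power comes from the non-central F distribution with non-centrality λ.

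**1. Reproducing 180.** Totals are the smallest multiple of 4 reaching 0.80.
- One-way ANOVA: λ = f²N, df 3 and N − 4. At N = 180, λ = 0.0625 × 180 = 11.25 and power is 0.804. At N = 176 it is 0.794. The answer is 180.
- Mixed ANOVA, between-groups effect: λ = f²N·m/(1 + (m − 1)ρ), with m = 3 measurements. N = 124, 144 and 168 at ρ = 0.5, 0.7 and 0.9. It reaches 180 only as ρ approaches 1, where the test reduces to the one-way F test.
- Mixed ANOVA, interaction: λ = f²N·m·ε/(1 − ρ), df 6ε and 2(N − 4)ε. N = 40, 48 and 64 at ρ = 0.5 with ε = 1, 0.75 and 0.5.
- Interaction with the effect size on the alternative scale, λ = f²N(m − 1)ε: N = 116, 136 and 180 at ε = 1, 0.75 and 0.5. The last again coincides with the one-way test.

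So 180 fits the one-way test exactly. It fits the named mixed design only at extreme settings.

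**2. Can an ANOVA of end values answer the mid-to-end question?** Hold the end-of-intervention effect at f = 0.25 and vary how much of it arises after the middle measurement. For end minus mid, the effect size is g/√(2(1 − ρ)), with g = 0.25, 0.125 or 0 for all, half or none after mid; df 3 and 176.

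| Mid-end correlation ρ | All after mid | Half | None | ANOVA of end values, every case |
|---|---|---|---|---|
| 0.1 | 0.527 | 0.155 | 0.05 | 0.804 |
| 0.3 | 0.646 | 0.189 | 0.05 | 0.804 |
| 0.5 | 0.804 | 0.254 | 0.05 | 0.804 |
| 0.7 | 0.962 | 0.407 | 0.05 | 0.804 |

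The last column is constant: the end-value test cannot tell the three cases apart. A one-way ANOVA of the change score could, but none is described.

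**3. Value of the baseline outcome.** Adding it as a covariate gives λ = f²N/(1 − ρ²), df 3 and 175, where ρ is now the baseline-end correlation. At ρ = 0.1, λ = 11.25/0.99 = 11.36 and power is 0.808. At 0.3, λ = 12.36 and power is 0.843. At 0.5, λ = 15.00 and power is 0.911. At 0.7, λ = 22.06 and power is 0.983. The comparator is 0.804.

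**4. Cost of leaving ANCOVA conditional.** Suppose, as an assumption, that ANCOVA is used when any of the six pairwise baseline t-tests has p < 0.05. In simulation (6,000 runs per scenario) this fires by chance in about 21% of trials per outcome. At correlations 0.3, 0.5 and 0.7, power is about 0.82, 0.82 and 0.85, against 0.84, 0.91 and 0.98 if the adjustment is pre-specified. Type I error is about 0.048, 0.041 and 0.024, which is conservative.

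**The case against.** **The time point is implied.** Post hoc tests belong to the ANOVA they follow, and those tests are placed at end of intervention. This stands, and that reading is adopted here; stating the time point is a clarification. It does not help the mid-to-end question, because on this reading the middle measurement enters no described test.

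**The ANCOVA trigger can be guessed.** The baseline balance checks come earlier in the same section, and candidate confounders are named elsewhere. This stands in part. What is missing is a working criterion and a final covariate list, and under the plausible trigger the quantified cost is precision only.

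**Baseline adjustment is a preference.** It is a recommendation on precision, not the correction of an invalid analysis. It is worth making because the data are already planned and the cost is almost nil.

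**A reader might infer** that the mismatch leaves the trial underpowered, that the comparison is biased, or that the conditional ANCOVA inflates false positives. The documents support none of these. The figure of 180 gives 0.804 for the one-way test. Randomisation protects the unadjusted end comparison. The conditional rule, as simulated, errs on the conservative side.

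**Conclusion.** The concern holds in three limited parts. First, the test named for sizing and the test named for analysis differ, and 180 agrees with the second; the sample-size text does not explain its own number. Second, the stated reason for the mid and end measurements has no described analysis, and an ANOVA of end values cannot supply one. Third, baseline outcomes are used only for balance testing, and ANCOVA depends on an undefined condition. For the third, the end-point power forgone ranges from almost nothing (0.804 against 0.808) to substantial (0.804 against 0.983) over assumed correlations of 0.1 to 0.7.

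These figures rest on 180 complete cases, f = 0.25 at end of intervention, and correlations that the documents do not give. The finding does not rest on those figures: the mismatch and the unanswered question are visible in the text alone. It should be fixed before analysis; it does not call the design or the enrolment target into question.

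**What to change.** In Statistical Analysis, replace the one-way ANOVA and conditional-ANCOVA sentences with one pre-specified linear mixed model per outcome:

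- **Model:** mid and end values as the response; fixed effects for group, time, group × time, the baseline value of that outcome, baseline × time, and academic year (the randomisation stratum); unstructured covariance.
- **Main test:** the group comparison at end of intervention.
- **Secondary:** the group contrast on end minus mid, with the mid-to-end change and its 95% confidence interval in each group. This covers both readings of further benefit.
- **Population:** students analysed in their assigned group. Baseline is measured at the workshop, after randomisation, so state how a missing baseline value is handled, for example by simple imputation of the covariate.
- **Baseline tables:** descriptive only, with no significance test choosing the model.
- **Coping and fear of blood sampling:** added in one pre-specified sensitivity analysis. This assumes that both are measured at baseline; Instruments and Covariates do not give their timing, so it should be stated.

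A simpler alternative is to name the sample-size section's mixed ANOVA in Statistical Analysis and add an explicit mid-to-end contrast.

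Either way, align the sample-size section with the chosen test and state the effect, correlation, epsilon and G*Power option behind 180.

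**Cost:** rewording and slightly more analysis, with no change in enrolment. No new data are needed if coping and fear are indeed collected at baseline. The end-minus-mid contrast may be underpowered (0.155 to 0.407 if half the benefit comes after mid), which is why it is labelled secondary.
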